**Protocol: Acceptance and Commitment Therapy for Tobacco Cessation Initiated in a Psychiatric Partial Hospital**

**NCT#: NCT03911960**

**Version Date: September 4th, 2019**

## BACKGROUND

There is a significant disparity in tobacco use among those living with mental illness. Individuals with mental illness are more likely to use tobacco, smoke more cigarettes per day, and experience more difficulty quitting than those without mental illness. Individuals living with serious mental illness (SMI, a mental illness meeting DSM criteria and resulting in substantial functional impairment, e.g., schizophrenia) die, on average, 20-25 years earlier than those without; these deaths are, in large part, attributable to smoking related diseases. Despite similar levels of motivation to quit, tobacco use in individuals without mental illness is declining while tobacco use in those with mental illness has remained steady. These steady tobacco use rates indicate that either existing treatments do not work for smokers with mental illness or that effective treatments are not reaching these individuals.

There is a knowledge deficit as to which treatments work for smokers with mental illness. Individuals with SMI are excluded from the majority of clinical trials, so many treatments have not been tested with this population. However, there has been research to support the use of provider intervention, pharmacotherapy, and mental health-tailored telephone counseling with smokers with mental illness. In contrast, public health campaigns and other population level interventions aimed at the general population are not effective for smokers with mental illness.

Mental health providers do not systematically address smoking. Mental health providers, have among the lowest levels of intervention around tobacco use of any healthcare providers. Among psychiatrists, rates of intervention around tobacco use have actually declined over time. Treatment models that encourage intervention with tobacco use in mental health treatment settings are needed.

Partial hospitalization is an excellent and underused opportunity to engage patients in tobacco treatment. Inpatient hospital systems provide a good setting to initiate intervention with tobacco use because, unlike private practice, they provide a closed system of providers who see large numbers of patients. By training a few clinicians to intervene and having a system for follow-up, tobacco treatment initiated in this setting could reach a large number of patients. Individuals hospitalized in a psychiatric hospital report high levels of motivation to quit. Two clinical trials of a computerized, stage-based, tobacco cessation treatment administered in inpatient psychiatry found that smokers were interested in tobacco treatment (recruitment rates 69-79%) and that those in the intervention group were more likely to be abstinent following hospitalization than usual care. Post-discharge abstinence rates were low, but increased over time. No safety concerns were found.

Partial hospital programs provide intensive day treatment for individuals in acute psychiatric distress. PHPs are prevalent; in 2010, there were over 400 programs nationwide. Partial hospitals may be an even better place to intervene with tobacco use than inpatient units because: (1) like inpatient psychiatry, there is a closed system of providers who can be trained; (2) patients are accessible; (3) patients are more stable in their illness than inpatients and therefore may be more able to accept and benefit from smoking cessation interventions; (4) partial hospital programs provide a context that allows for goal setting and restructuring of patients' home environments; (5) patients spend the day on a smoke free campus which may reduce opportunities to smoke and provide practice managing cravings; (6) patients go home at night and are encouraged to practice skills that they have learned in their home environment.

Acceptance and Commitment Therapy (ACT) is a promising treatment strategy for smokers living with SMI. ACT is a third wave cognitive behavioral therapy with two key components: (1) acceptance of unpleasant thoughts, feelings or sensations, and (2) commitment to values-guided action despite discomfort. ACT is a general psychotherapeutic approach that has been used successfully to treat a variety of mental health diagnoses including anxiety, depression, and psychosis.

Several pilot studies show promise for ACT as a treatment for tobacco dependence, including one showing favorable results compared to traditional cognitive behavioral approaches. To date, no large scale (fully powered) trials have been completed on the use of ACT for tobacco cessation.

Most of the ACT for smoking cessation studies have included only non-psychiatric populations. ACT may be particularly well-suited for tobacco cessation in patients with psychiatric comorbidities as: (1) ACT treatments can also be applied to treat mental health symptoms allowing for a consistent treatment framework across diagnosis, (2) the hypothesized mechanism of change (i.e., willingness to experience distress and discomfort in order to live a valued life) may be particularly relevant for smokers with psychiatric comorbidities, who are more dependent and have more severe withdrawal symptoms (i.e., they will experience more

discomfort than average when quitting). There have been two, small, uncontrolled, feasibility studies of ACT for smoking cessation in patients with mental illness. These studies found ACT for tobacco cessation to be feasible in smokers with bipolar disorder and posttraumatic stress disorder. There have been no controlled trials of ACT for smoking cessation in patients with psychiatric comorbidities. More work is needed to assess the feasibility of applying the ACT treatment approach to tobacco cessation treatment with smokers with SMI, particularly among those in acute psychiatric episodes.

**SUBJECT RECRUITMENT:** Source. Participants will be recruited from the Rhode Island Hospital (RIH), Psychiatric Partial Hospitalization program (PHP; See letter from [name], Medical Director of the program). This day treatment program (8AM-2PM) employs the principles of ACT via four group sessions, and individual meetings with both a psychologist and a psychiatrist.

Sample size. We propose a sample size of 20 smokers per group because the primary aim of the R03 grant mechanism is to assess initial feasibility. We will oversample men such that 50% of the sample is male. Based on the current census of the PHP, we anticipate 240 smokers will be seen over the 8-month recruitment period, making it feasible to recruit 40 smokers.

Inclusion criteria. Participants will be male and female, current daily smokers,  $\geq$  age 18, have regular telephone access, and are able to read and write English.

Exclusion criteria will be: current use of tobacco cessation treatment (bupropion prescribed for a psychiatric indication will be permitted). In order to participate in the PHP, patients must speak English (as groups are offered in English only). If participants would like the nicotine patch, they must be free of medical contraindications to the nicotine patch (unless a medical provider gives approval; contraindications include recent (<2 weeks) myocardial infarction, serious underlying arrhythmias, serious or worsening angina pectoris, and pregnancy or breastfeeding).

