## PROCEDURES:

Recruitment. Participants will be recruited during PHP treatment. As standard clinical care, all patients are screened for smoking status upon admission. Current daily smokers will be informed about the study at that time and invited to be screened for participation. All women of childbearing potential who would like the nicotine patch will complete a pregnancy test prior to inclusion into the study. Eligible and interested participants will complete an enrollment/pre-quit visit while enrolled in the PHP, which includes a baseline assessment, random assignment to a condition, the first counseling session and 4 weeks of nicotine patches (to be started on the quit day). The enrollment visit can be on the same day as the first pre-quit visit counseling but doesn't need to be. Participants will then complete a second pre-quit counseling session (within one week of the pre-quit session but before discharge). If the participant is to be discharged before their first or second counseling session, the counselor will choose one of the following options in order of preference ((1) complete the second counseling session early but not on the same day as the first counseling session,(2) have the patient return to the partial hospital program location for the first or second counseling session, (3) complete the counseling session by phone and mail materials distributed during the counseling session). Following the second counseling session, participants will continue in their assigned post-discharge intervention consisting of up to 5 Quitline or ACT telephone sessions.

Study outcomes will be assessed at the end of the counseling treatment at an in-person visit 5 weeks after their visit 2 date OR 24 hours after the last counseling session by a research staff member, whichever is later. As an incentive for completion of the follow-up assessment, those in either group who complete this visit will receive \$20 compensation and an additional 4 weeks of the nicotine patch. We will try to schedule visits around existing appointments in the hospital system to increase compliance.

Randomization will use block randomization, unknown to the counselor or the participant. In order to balance any benefit of bupropion treatment in combination with the nicotine patch across treatment conditions, randomization will be stratified by bupropion use.

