#### Measures.

Feasibility, acceptability and safety. Feasibility of recruitment and retention will be measured by the proportion of smokers seen in the program during the enrollment period who enroll during the recruitment period. The two existing studies of smoking cessation treatment provided in inpatient psychiatric hospitals reported 69-79% recruitment rate (of those meeting inclusion criteria) and 80% retention. Results in this range will be considered feasible. Feasibility of treatment delivery will be assessed by the number of completed visits in the ACT group. Previous studies of ACT for tobacco cessation have found approximately 65-67% of calls were completed. Results in this range will be considered feasible. Acceptability will be measured at end of treatment using the 8-item Client Satisfaction Questionnaire (CSQ), a reliable and valid questionnaire developed to test health program acceptability. Safety. We will collect information on patient re-hospitalization via chart review and using questions from the 2016 National Health Interview Survey about visits to the emergency room and to the hospital. In addition, we will assess for symptom exacerbation. In addition, we will measure global distress using the K6 scale, a measure of non-specific psychiatric distress that has been used in population samples to discriminate between samples with and without mental illness.

Efficacy. Efficacy will be measured by 7-day point-prevalence tobacco abstinence at end of treatment, verified by an expired breath CO rating  $\leq 6\text{ppm}$ . Finally, we will assess number of serious quit attempts ( $>24$  hours of intentional abstinence).

ACT treatment targets. ACT treatment targets will be measured at both in person visits and during the follow-up call. The two overarching constructs of ACT, acceptance, and commitment will be assessed. Acceptance, will be measured using the Avoidance Inflexibility Scale (AIS), a 13 item, Likert scale, assessing participants' responses to their internal stimuli, including smoking-related thoughts, feelings and physiological sensations. Acceptance has been shown to account for the bulk of the treatment effect of ACT for tobacco cessation in previous studies. Commitment will be measured using the 8-item, Commitment to quitting scale (CTQ).

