Study Title: Acceptance and Commitment Therapy for Tobacco Cessation Among Psychiatric Partial hospital Patients

NCT#: NCT03911960

Date: July 1st, 2020

Data analysis.

Due to small sample sizes, analyses will be descriptive.

Aim 1. To assess the feasibility of the proposed ACT-based counseling program, we will conduct descriptive statistics on number of patients recruited to the program during the enrollment period compared to number of smokers seen in the PHP during the enrollment period. In addition, we will conduct descriptive statistics on the number of sessions completed per group and rates of completion of the follow-up visit. To assess acceptability of the program, we will report descriptive statistics of responses on the Client Satisfaction Questionnaire in each group. To evaluate the safety of offering a tobacco cessation intervention during a PHP, we will report on the number of participants in the trial who are rehospitalized for a psychiatric reason during the treatment period based on participant self-report at end of treatment. To assess for symptom exacerbation we will report means of psychiatric symptoms by group pre and post intervention among those who completed follow-up.

Aim 2. To evaluate for preliminary evidence of efficacy, we will report abstinence rates by group at end of treatment. Those lost to follow-up will be considered smokers.

Aim 3. To assess for the effect of treatment condition on ACT treatment targets, we will report descriptive statistics of treatment targets before treatment and at follow-up for those who completed the follow-up visit.

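### Recruitment feasibility counts smokers who could not be offered a place as not recruited, because 40 capped places, half of them for men, are scored against all smokers seen and then judged by a benchmark for eligible smokers

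*Protocol*

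**What the plan says.** **Size and sex mix.** Under Subject Recruitment, Sample size, the protocol states "We propose a sample size of 20 smokers per group", so 40 in all, and then "We will oversample men such that 50% of the sample is male". It continues: "we anticipate 240 smokers will be seen over the 8-month recruitment period, making it feasible to recruit 40 smokers". It gives neither the share of men among smokers in the partial hospital program (PHP) nor the method of oversampling.

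**Approach.** Under Procedures, Recruitment: "Current daily smokers will be informed about the study at that time and invited to be screened for participation". No condition on sex is attached.

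**Measure.** The Measures section defines recruitment feasibility as "the proportion of smokers seen in the program during the enrollment period who enroll during the recruitment period". SAP Aim 1 uses the same ratio: "number of patients recruited to the program during the enrollment period compared to number of smokers seen in the PHP during the enrollment period". Neither splits it by sex or sets aside smokers for whom no place was available.

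**Benchmark.** The Measures section cites two inpatient studies that "reported 69-79% recruitment rate (of those meeting inclusion criteria) and 80% retention" and treats results in that range as feasible. The SAP repeats no pass range and describes all its analyses as descriptive.

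**The concern.** The measure is meant to show whether smokers in this setting will join such a trial. Its numerator cannot exceed 40 by design, while its denominator grows with every smoker seen, including those to whom the trial had nothing left to offer. The result therefore reflects the number of places and the length of screening as well as willingness to enrol.

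The sex target can add to this. Oversampling men implies that men are under half of PHP smokers. A 50% male sample of 40 is 20 men and 20 women. If women's enrolment is held back to reach that balance, eligible and willing women stay in the denominator as failures while men's places are filled.

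At stake is the reading of a main feasibility outcome that has a stated pass range. A program with uptake inside 69-79% could be reported as falling short of it.

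**Working it through.** **Inputs from the documents.** Places: 2 x 20 = 40, which reproduces the protocol's total. Male target 50%: 0.5 x 40 = 20 men, leaving 20 women. Smokers expected over 8 months: 240. Benchmark: 69-79% of those meeting inclusion criteria.

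**Inputs assumed.** Men's share of PHP smokers, m, is not given; I use 0.35 to 0.45, with 0.50 as a control. True uptake when a place is open, w, is 0.74, the middle of the benchmark, and equal in both sexes. All smokers seen are taken as eligible, which favours the plan's measure.

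**Step 1: the plan's own figures.** Scored rate = 40/240 = 16.7%. A rate of 69-79% of 240 would need 0.69 x 240 = 165.6 to 0.79 x 240 = 189.6 enrolled, about 166 to 190, against 40 places. Once uptake is enough to fill 40 places, the scored rate no longer depends on it.

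The sex target hardly changes this. Filling 20 men's places from 240 smokers needs an expected 240 x m x w of at least 20. At m = 0.35 that is w of at least 20/(240 x 0.35) = 23.8%. Simulated with 240 seen, w = 0.74 gives 16.7% with and without the target for m = 0.35, 0.40 and 0.45. At w = 0.25 and m = 0.35 it gives 16.1% against 16.7%.

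**Step 2: an eligible-only denominator.** If a share e of the 240 is eligible, the rate is 40/(240e). It lies in 69-79% only if e is between 40/(0.79 x 240) = 21.1% and 40/(0.69 x 240) = 24.2%. Matching the benchmark's denominator is therefore not enough by itself; the cap on places must also be dealt with.

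**Step 3: recruitment that stops when the sample is full.** Suppose instead that counting ends once 20 men and 20 women are enrolled, with each sex closed at 20. Filling the men's places takes about 20/(m w) smokers seen, so the scored rate is about 40/[20/(m w)] = 2 m w. This ignores the chance that women's places fill last, so I also simulated it.

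| m | 2 m w (w = 0.74) | Simulated mean seen | Simulated mean rate | Chance of 69% or more |
|---|---|---|---|---|
| 0.35 | 51.8% | 77 | 54% | 7% |
| 0.40 | 59.2% | 68 | 60% | 18% |
| 0.45 | 66.6% | 63 | 65% | 31% |
| 0.50 | 74.0% | 61 | 67% | 37% |
| No sex target | n/a | 54 | 74% | about 79% |

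The 0.50 row is the control. There men need no oversampling, yet the rate falls from 74% to 67% because the stop at exactly 20 + 20 makes one sex wait for the other. Only the fall from 67% to 54-65% is due to men being under half of smokers, and at m = 0.45 that is about 2 points.

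**Step 4: the corrected denominator.** Counting each smoker only if a place for their sex was open when they were seen, the same simulation returns a mean of 74%, with about a 79% chance of reaching 69%, at every m in the table.

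**The case against.** The strongest objection is that the closing of women's places is not in the documents. The protocol sets a target of 50% men and says daily smokers will be invited, with no sex condition. The balance could be reached loosely or through extra effort to recruit men, with no woman refused. This stands: the text supports saying that the method is not stated, not that women will be turned away.

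A reader might also infer that the sex target by itself makes a feasible program look infeasible. The documents do not support that. On the protocol's 240 smokers the rate is 16.7% either way. The lower rates in Step 3 arise only if recruitment ends after about 63 to 77 smokers, which at 240/8 = 30 a month is 2.1 to 2.6 months of the planned 8. Part of that loss also comes from the rigid 20 + 20 stop. In reply, the protocol offers 240 as evidence that 40 can be found and does not say that counting continues once places are full, so the early-stop case cannot be excluded.

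Finally, the analyses are descriptive and the SAP states no pass mark. No test, power calculation or efficacy result changes. That limits the importance of the point, but the protocol's feasibility range remains and would be applied to a number that cannot reach it under the plan's own figures.

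**Conclusion.** The point holds as a fault in how recruitment is scored. The denominator includes smokers who had no chance of enrolling, and the benchmark was measured on a different denominator. The fixed total of 40 against all smokers seen is the main cause, giving 16.7% at the protocol's own figures. The sex target is a secondary cause that matters only if women are limited and recruitment stops when the places are full. In that case a true 74% would score about 54-65% at an assumed men's share of 0.35-0.45.

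Those last figures rest on an assumed men's share, equal uptake in both sexes, first-come enrolment and a hard stop at 20 + 20. The 16.7% rests only on the protocol's numbers and on the places being filled. The consequence is confined to the descriptive recruitment outcome and its feasibility label.

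**What to change.** In the protocol's Measures section and in SAP Aim 1:

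- State how men will be oversampled, including whether and when enrolment of women is limited, and when counting of smokers seen ends.
- Record for each smoker in the screening log: sex, date seen, eligibility, whether a place open to that person was available, and whether it was offered.
- Compare with 69-79% the rate enrolled / eligible smokers seen while a place open to them was available, overall and by sex. Report the all-smokers figure beside it.

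No reweighting to the program's sex mix is needed.

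The cost is a few extra log fields and some wording; smoking status is already screened at admission, and no extra patients are required. The denominator will be smaller, so the rate will be less precise, especially by sex with about 20 enrolled in each.

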## PROCEDURES:

Recruitment. Participants will be recruited during PHP treatment. As standard clinical care, all patients are screened for smoking status upon admission. Current daily smokers will be informed about the study at that time and invited to be screened for participation. All women of childbearing potential who would like the nicotine patch will complete a pregnancy test prior to inclusion into the study. Eligible and interested participants will complete an enrollment/pre-quit visit while enrolled in the PHP, which includes a baseline assessment, random assignment to a condition, the first counseling session and 4 weeks of nicotine patches (to be started on the quit day). The enrollment visit can be on the same day as the first pre-quit visit counseling but doesn't need to be. Participants will then complete a second pre-quit counseling session (within one week of the pre-quit session but before discharge). If the participant is to be discharged before their first or second counseling session, the counselor will choose one of the following options in order of preference ((1) complete the second counseling session early but not on the same day as the first counseling session,(2) have the patient return to the partial hospital program location for the first or second counseling session, (3) complete the counseling session by phone and mail materials distributed during the counseling session). Following the second counseling session, participants will continue in their assigned post-discharge intervention consisting of up to 5 Quitline or ACT telephone sessions.

Study outcomes will be assessed at the end of the counseling treatment at an in-person visit 5 weeks after their visit 2 date OR 24 hours after the last counseling session by a research staff member, whichever is later. As an incentive for completion of the follow-up assessment, those in either group who complete this visit will receive \$20 compensation and an additional 4 weeks of the nicotine patch. We will try to schedule visits around existing appointments in the hospital system to increase compliance.

Randomization will use block randomization, unknown to the counselor or the participant. In order to balance any benefit of bupropion treatment in combination with the nicotine patch across treatment conditions, randomization will be stratified by bupropion use.

Participant payment. Participants will be paid \$20 for the enrollment/pre-quit visit and \$20 for the follow-up assessment visit. If the first counseling session happens by phone, participants will be paid for the assessment with a mailed gift card with a \$20 value, instead of \$20 cash. Participants will be paid \$5 per telephone counseling session completed. Payment for the counseling sessions will be paid at the follow-up visit and is contingent on follow-up visit attendance.

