## Interventions.

Nicotine patch. All participants will receive usual psychiatric care plus an offer of the nicotine patch (up to 8 weeks), dosed per package instructions. At the second pre-quit session, participants will be instructed on patch use. The first 4 weeks of patch will be distributed at enrollment and the second 4 weeks will be distributed at the follow-up visit.

Enhanced Usual Care (EUC). Participants in the EUC condition will receive one in-person counseling sessions during the PHP and a second telephone session the week following: the first session will occur prior to the quit day and will focus on establishing a quit plan and instructing the participant on the use of the nicotine patch; the second session will occur prior to quit day and will assess for any difficulties using the nicotine patch. After the second session, participants will be electronically referred to the RI state quitline. This quitline offers an enrollment call and 5 proactive counseling telephone counseling telephone calls to those who enroll. Quitline staff make up to 3 attempts per call to reach users. Total scheduled counseling time offered is 120 minutes. If the participant is unexpectedly discharged before their first counseling visit, the counselor will choose one of the following options in order of preference ((1) complete the second counseling session early but not on the same day as the first counseling session,(2) have the patient return to the partial hospital program location for the first counseling session, (3) complete the counseling session by phone and mail materials distributed during the counseling session).

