#### RISKS:

Nicotine patch side effects: All subjects who are ready to quit have no contraindications to the patch will be offered an 8-week supply of free nicotine patches. The nicotine patch has been in clinical use for almost 20

years. It is available over the counter and has been judged to be generally safe and efficacious with very few contraindications. If the participant has a medical contraindication to the nicotine patch (e.g., recent history of MI) he or she must obtain clearance from a medical provider in order to receive the patch from the study team (e.g., their PHP psychiatrist or their primary care provider). Initial dosing will follow package instructions. Study counselors will explain the patch's purpose, application, and side effects. Common side effects of the patch include local skin irritation at the site of the patch, nausea if the dose is too large or if the participant continues to smoke at a high level while using the patch, and disturbed and vivid dreams. Less common reactions include allergic reactions. A comprehensive meta-analysis of 129 studies involving 177,390 individuals concluded that there was no significant difference between Nicotine Replacement Therapy and placebo in prevalence of severe adverse events (SAEs) including suicidal ideation, heart attack, and mortality. Thus, the principal investigator of this study, [name]. expects the risk of using the nicotine patch in the current study be very minor. We will obtain a release to inform participants' psychiatric and primary care providers that they have enrolled in a tobacco cessation study and may have been started on the nicotine patch. Participants can call the study PI or their medical provider for information on managing side effects of the nicotine patch.

Nicotine Withdrawal Symptoms After Quitting: There is a strong likelihood that most study participants who quit smoking will experience some nicotine withdrawal symptoms, including anxiety, restlessness, anger, irritability, sadness, problems concentrating, appetite change and weight gain, insomnia, and decreased heart rate. Generally, these reactions are temporary and pose no serious health risks.

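### No contraindication check is scheduled before the second 4-week patch supply, which is handed out at least 35 days after the enrollment checks

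*Protocol*

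**What the plan says.** **The rule.** The exclusion criteria (Protocol, SUBJECT RECRUITMENT) state: "If participants would like the nicotine patch, they must be free of medical contraindications to the nicotine patch". A medical provider's approval lifts the restriction. The contraindications named are a myocardial infarction in the past two weeks, serious arrhythmia, serious or worsening angina, pregnancy and breastfeeding. RISKS (Nicotine patch side effects) repeats the rule. Participants who are ready to quit and "have no contraindications to the patch will be offered an 8-week supply of free nicotine patches". Someone with a contraindication may still be supplied, but "he or she must obtain clearance from a medical provider in order to receive the patch from the study team".

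**The checks.** PROCEDURES (Recruitment) places the pregnancy test before entry: "All women of childbearing potential who would like the nicotine patch will complete a pregnancy test prior to inclusion into the study". PROTECTION AGAINST RISK (Minimization of nicotine patch side effects) says participants are screened for contraindications, with provider approval needed before they take part. It states no repeat.

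**The supplies.** Interventions (Nicotine patch) says: "The first 4 weeks of patch will be distributed at enrollment and the second 4 weeks will be distributed at the follow-up visit". PROCEDURES sets that visit "at an in-person visit 5 weeks after their visit 2 date OR 24 hours after the last counseling session", whichever is later. It promises participants who complete the visit $20 "compensation and an additional 4 weeks of the nicotine patch", and that sentence attaches no condition to the patch.

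**After enrollment.** Under PROTECTION AGAINST RISK, participants agree to ask their outpatient providers about patch safety if their medical status changes once they have the patch. Those with severe side effects are asked to stop the patch and contact primary care. Providers are told of the quit attempt by a letter faxed at enrollment.

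**The concern.** The study dispenses patch twice but schedules its checks once. Every listed contraindication can arise after enrollment. The infarction criterion looks back only two weeks, so a screen done five or more weeks earlier says nothing about it on the day of the second supply. Pregnancy and breastfeeding are the clearest gap, because no other planned step at follow-up is aimed at finding them.

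What is at stake is participant safety on a small scale. A member of staff following the protocol text could give four more weeks of patch to someone who has become contraindicated, without knowing it and without the provider approval that the protocol itself requires.

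**Working it through.** The plan gives no figure of its own here. The check is date arithmetic, a count of supplies, and a comparison of the rule with the steps that apply it.

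**1. Shortest time from enrollment checks to second supply.** Inputs are from PROCEDURES. Follow-up is the later of visit 2 plus 5 weeks and the last counseling session plus 24 hours. The second session is within one week of the first and, if brought forward, is not on the same day. Put enrollment at day 0, with the checks on or before that day, and visit 2 at day v.

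- Follow-up day = max(v + 5 × 7, last session + 1), which is at least v + 35.
- If visit 2 is read as the enrollment day, v = 0: at least day 35.
- If visit 2 is the second counseling session, v is at least 1: at least day 36.
- If that session is 7 days after a same-day enrollment and first session, v = 7: at least day 42.

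A late last session, or a first session held after the enrollment day, only lengthens the gap. At least 35 days therefore holds under every reading of visit 2.

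**2. How far use could extend.** A full second supply lasts 4 × 7 = 28 days. Started on the day it is given and used in full, it ends at 35 + 28 = day 63, or 36 + 28 = day 64, and later if follow-up is later. The patch is an offer of up to 8 weeks, so a participant may stop sooner or never start.

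**3. The infarction window.** The criterion covers 14 days. At a day-35 visit the relevant period starts at day 35 − 14 = 21. All of it falls after the enrollment screen.

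**4. How many second supplies.** Inputs: 40 participants with men oversampled to 50% (Sample size); 80% retention in the inpatient studies cited under Measures; 67% retention in the telephone study cited under ACT Care. Assumptions: the other half are women, retention is equal by sex, and every completer takes the supply.

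| Retention | Second supplies | Of which to women |
|---|---|---|
| 100% | 40 | 40 × 0.50 = 20 |
| 80% | 40 × 0.80 = 32 | 16 |
| 67% | 40 × 0.67 = 26.8, about 27 | 13.4, about 13 |

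These are upper limits on people supplied at each retention rate. They do not count people with a new contraindication. Some participants will not want the patch, and not every woman is of childbearing potential.

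**5. The rule beside the steps.**

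| Step | First supply | Second supply |
|---|---|---|
| No contraindication, or provider approval | Required | Required (the rule has no time limit) |
| Contraindication screen by study staff | Planned | None scheduled |
| Pregnancy test if patch is wanted | Planned | None scheduled |
| Participant consults own provider on a change | Not applicable | Relied on |

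The hospital and emergency room questions under Measures (Safety) could bring an infarction to light. They are collected as safety outcomes, nothing in the protocol links them to dispensing, and they do not ask about pregnancy or breastfeeding as such.

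**The case against.** The best case for the plan is that it does cover the period after enrollment. Participants undertake to consult their providers if their status changes, the clearance rule under RISKS has no expiry and so governs the second supply too, and providers have been told about the study. The product is sold over the counter and described as generally safe, with few contraindications. Pregnancy is not an absolute bar, since a provider may approve use. The documents cite no standard that requires re-testing before a second supply. The protocol also mentions separate study manuals, which may contain dispensing steps that are not visible here.

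Much of this stands, and it is why the point is minor. What it does not supply is current information for the person dispensing. The duty to consult depends on the participant noticing a change and acting on it, which an unrecognised pregnancy would defeat. The clearance rule can be applied only if someone asks.

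Several stronger readings are tempting, and the documents do not support them:

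- **That the protocol permits patch for contraindicated participants at follow-up.** It does not. The rule applies; the missing piece is a step to apply it.
- **That Table 2 shows the checks were left out at end of treatment.** Table 2 lists study measures. It omits the screen and the pregnancy test at enrollment as well, where both are planned, so its silence shows nothing.
- **That patch use runs to at least day 63 or 64.** That is the earliest end of a fully used second supply, not a minimum for use.
- **That a woman who declined patch at enrollment would receive it untested at follow-up.** The protocol does not say whether patch can be first taken up at that visit, so this is conjecture.

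**Conclusion.** The point holds as a minor safety improvement. The protocol text schedules the contraindication screen and pregnancy test only around enrollment, yet dispenses again at least 35 days later, relying in between on participants to raise any change with their own providers. The interval follows from the protocol's own visit rules and does not depend on how visit 2 is read.

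The ceiling is 40 second supplies, 20 of them to women, or 32 and 16 if the 80% retention seen in other studies applies. The number with a new contraindication cannot be computed and may be zero. The conclusion concerns the protocol text alone; a manual or consent form could already contain the step.

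A reader might infer some effect on the trial's results. There is none: the SAP's descriptive analyses of feasibility, acceptability, safety, abstinence and treatment targets are unaffected. A reader might also notice that PROTECTION AGAINST RISK ties provider approval to taking part, while the exclusion criteria and RISKS tie it to receiving patch. That is a separate editorial matter and adds nothing to this point.

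**What to change.** In the follow-up visit paragraph of PROCEDURES, add: *Before the second 4 weeks of patch are given to those who want them, staff repeat the contraindication questions in the exclusion criteria, including pregnancy and breastfeeding; anyone with a contraindication receives patch only with medical provider approval.* The $20 payment for the visit stays as it is.

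The cost is a few minutes at a visit already held in person, plus an IRB amendment, because the Monitoring section bars any change before IRB approval. No extra visits or participants are needed.

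A repeat pregnancy test for women of childbearing potential who want the second supply is optional. It would detect an unrecognised pregnancy, which questions alone would miss. It would mean at most 20 tests, or about 16 at 80% retention. It is an added procedure and needs a plan for positive results, covering disclosure and referral, at a visit run by research staff.
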